3.7. Efficacy Analyses

3.7.1. Efficacy Analysis

The following efficacy endpoints will be analyzed:

- Change from baseline in CGI-S score by visit
- Shift analysis in CGI-S
- Change from baseline in IWQOL-Lite scales (total score, physical function, self-esteem, sexual life, public distress, and work) by visit
- Time to treatment discontinuation

Value and change from baseline in CGI-S and IWQOL-Lite scores by visit will be summarized using descriptive statistics.

The IWQOL-Lite scale is a 31-item self-report measure of obesity-specific quality of life. IWQOL-Lite provides an overall total score as well as scores on five domains: (1) physical function, (2) self-esteem, (3) sexual life, (4) public distress, and (5) work. The raw scores will be transformed as follows (Tessier et al, 2012): the transformed scores range from 0 to 100, with 100 representing the best, and 0 representing the most impaired quality of life.

$$\text{Transformed Score} = \frac{\text{maximum theoretical score} - \text{actual score}}{\text{test score range}} \times 100$$

CGI-S response will be categorized into the categories summarized in [Table 1](#). The number and percentage of subjects in each category and with shifts from baseline will be summarized based on the observed data by descriptive statistics at 1, 3, 6, and 12 months. The shift categories are summarized in [Table 2](#).

Table 1: Definition of Shift CGI-S Categories

Response Category	CGI-S Score
Markedly to Extremely Ill	≥ 5
Moderately Ill	4
Normal to Mildly Ill	≤ 3

Table 2: Shift Categories for CGI-S response

Shift from Baseline Category for CGI-S Response	
Baseline Category	Shift Category
Markedly to Extremely Ill	
No change	
≥ 1 level improvement	
2 level improvement	
Moderately Ill	
No change	
1 level improvement	
1 level worsening	
Normal to Mildly Ill	
No change	
≥ 1 level worsening	
2 level worsening	

Time to treatment discontinuation will be analyzed using the Kaplan-Meier method and the KM plot will be provided. Both all-cause discontinuation and discontinuation due to AE will be summarized. For prematurely discontinued subjects (all cause or due to AE), time to event is defined as time from the date of first dose of study drug in study ALK3831-A308 to the date of last dose of study drug. Other subjects will be censored at the last dose of the study drug.

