3.8.1. Adverse Events

Incidence of treatment-emergent AEs (TEAEs) will be analyzed as a safety endpoint. Adverse events will be coded by System Organ Class and Preferred Term using the Medical Dictionary for Regulatory Activities (MedDRA[®]) Version 21.0 or higher. The verbatim term will be included in the AE listings.

An AE (coded by preferred term) will be considered a TEAE if the event is newly occurring or worsening on or after the date of first dose of study drug and within 7 days after the last dose of study drug in this study.

An overview table, including number of subjects with TEAEs, AEs leading to treatment discontinuation, study drug related TEAEs, and SAEs will be provided.

The number and percentage of subjects reporting TEAEs during the treatment period will be presented for the following categories:

- System organ class and preferred term
- Preferred term, and including the following subset:
 - TEAEs experienced by $\geq 2\%$ of subjects
- System organ class, preferred term, and severity
- System organ class, preferred term for severe TEAEs
- System organ class, preferred term, and relationship
- System organ class, preferred term for study drug related TEAEs

If the same preferred term occurred more than once for the same subject, the subject will be counted only once for that preferred term using the most severe and most related occurrence for the summarization by severity and by relationship to the study drug.

In addition, the number and percentage of subjects reporting AEs during the safety follow-up period will be tabulated by the system organ class and preferred term.

Subgroup analysis by age (<40 years vs ≥ 40 years), sex (Female vs Male) and race (Black or African American, White, and Other) will be performed for TEAEs during the treatment period by preferred term.

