6.2. Handling of Partial Dates of Concomitant Medication and Adverse Events

Partial start dates of prior, concomitant medications, and adverse events will be assumed to be the earliest possible date consistent with the partial date. Partial stop dates of prior, concomitant medications, and adverse events will be assumed to be the latest possible date consistent with the partial date. In the case of completely missing stop date, medication will be assumed to be ongoing.

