APPENDIX 6. COVID-19 ANALYSIS

Pandemic has resulted in certain disruptions in the study conduct since early 2020, including site closure, delayed study drug supply, subjects discontinuation and missing assessments. These impacts were limited in scope upon review of the protocol deviations, and also confounded by the initiation of new regions. Sites in Ukraine and Russia were first initiated in March 2020 and July 2020. Therefore, only descriptive statistics will be provided to explore the potential impact of the pandemic on the primary and secondary objectives of the study. The following subgroup analysis (before vs during pandemic) will be conducted:

- Disposition
- Demographics and Baseline Characteristics
- Protocol Deviation
- Primary Efficacy Endpoint
- Key Secondary Endpoints
- TEAE
- SAE

Subjects enrolled before 01 Mar 2020 will be grouped as before pandemic, and subjects enrolled after this date will be grouped as during pandemic. While the pandemic has started in various regions a few weeks apart, a single cutoff date will be applied.

Signature Page for CLIN_ALK3831-A308-sap

Approved	Name: PPD Capacity: Other Date: 04-Dec-2023 19:59:22 GMT+0000
Approved	Name: PPD Capacity: Clinical Date: 04-Dec-2023 23:33:04 GMT+0000
Approved	Name: PPD Capacity: Clinical Date: 07-Dec-2023 12:34:29 GMT+0000
Approved	Name: PPD Capacity: Other Date: 07-Dec-2023 13:00:52 GMT+0000

Alkermes® Confidential Information

Document REG-026019

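### SAP Appendix 6 splits subjects by enrolment date, so pandemic-time adverse events, deviations and discontinuations of earlier enrolees are counted as before the pandemic

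*SAP*

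**What the plan says.** SAP Appendix 6 lists pandemic disruptions since early 2020: closed sites, late drug supply, discontinuations and missed assessments. It plans a descriptive before-versus-during comparison of disposition, baseline characteristics, protocol deviations, efficacy endpoints, TEAEs and SAEs. The groups are set by enrolment date alone: "Subjects enrolled before 01 Mar 2020 will be grouped as before pandemic, and subjects enrolled after this date will be grouped as during pandemic".

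The appendix states its own limits. On the disruptions it says "These impacts were limited in scope upon review of the protocol deviations", and it calls them "confounded by the initiation of new regions", noting that "Sites in Ukraine and Russia were first initiated in March 2020 and July 2020". It also accepts one cutoff date for all regions. It does not say that earlier enrolees were followed into the pandemic.

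Nothing elsewhere dates an event against the cutoff. SAP 3.8.1 counts TEAEs from first dose to "within 7 days after the last dose of study drug in this study". SAP 3.7.1 times discontinuation from first to last dose, and "Other subjects will be censored at the last dose of the study drug". The Protocol Synopsis and Protocol 8.1 give 24 to 48 months of treatment, or until regulatory action. The study end is set 24 months after the last enrolment, targeted for Q4 2022.

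**The concern.** Site closures and supply delays affect whoever is in the study when they happen. A grouping fixed at enrolment does not follow them. A subject enrolled in 2019 who left because a site closed in 2020 would be tabulated as a *before pandemic* discontinuation, and the same holds for that subject's later adverse events and deviations.

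The *before* column therefore mixes pre-pandemic and pandemic time. The *during* column holds only later enrolees, including everyone from the newly opened countries. If the pandemic raised discontinuations or deviations in both groups, the two percentages could look alike and be read as no impact. At stake is how this appendix is read. The main safety and efficacy summaries are not affected.

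**Working it through.** The plan states no figure for this overlap, so there is nothing to reproduce. The check is date arithmetic followed by a range over assumptions.

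**Inputs from the documents.** Cutoff 01 Mar 2020 (SAP Appendix 6). First consent estimated Q2 2017 and last visit Q4 2022 (Protocol Synopsis). Treatment 24 to 48 months (Protocol 8.1). One month is 28 days (SAP 6.1), so 24 months = 672 days and 48 months = 1344 days.

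**Assumptions.** First enrolment 01 Apr, 15 May or 30 Jun 2017. Enrolment up to the cutoff uniform, linearly falling or linearly rising. Study end 01 Oct, 15 Nov or 31 Dec 2022. Exponential dropout with Month-24 retention R of 100, 70, 50 or 30%.

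**Step 1: who can reach the cutoff.**
- 01 Mar 2020 minus 672 days = 29 Apr 2018. Anyone enrolled after that who stays 24 months is on treatment at the cutoff.
- 01 Mar 2020 minus 1344 days = 26 Jun 2016, before first consent.
- A subject enrolled on 29 Feb 2020 and treated for 672 days spends 671 of them (99.9%) on or after the cutoff.

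**Step 2: central case without dropout.** Uniform enrolment from 15 May 2017 gives 1021 enrolment days before the cutoff. Let g be the days from enrolment to the cutoff (1 to 1021).
- *Courses of 672 days.* On treatment at the cutoff: 671/1021 = 66%. Treatment time after it: 671/(2 × 1021) = 33%.
- *Treated to the common end (15 Nov 2022, 989 days after the cutoff) or 1344 days.* Planned course T = min(1344, 989 + g), so all are on treatment at the cutoff. The 1344-day cap applies from g = 356 on. Time after the cutoff: 355 × 989 + Σ(1344 − g) for g = 356 to 1021 = 351,095 + 436,563 = 787,658 days. Total: Σ(989 + g) for g = 1 to 355, plus 666 × 1344 = 414,285 + 895,104 = 1,309,389 days. Share: 60%.

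**Step 3: add dropout.** The hazard is λ = −ln(R)/672. Expected treatment time to day t is (1 − exp(−λt))/λ, and the chance of still being on treatment at the cutoff is exp(−λg) when g < T. Central case:

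| Month-24 retention | On treatment at cutoff, common end | Time after cutoff, common end | On treatment at cutoff, 24-month course | Time after cutoff, 24-month course |
|---|---|---|---|---|
| 100% | 100% | 60% | 66% | 33% |
| 70% | 77% | 54% | 55% | 31% |
| 50% | 62% | 48% | 47% | 29% |
| 30% | 46% | 40% | 38% | 26% |

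With a constant hazard, the share of discontinuations falling after the cutoff equals the share of treatment time. At 70, 50 and 30% retention it is 54, 48 and 40% (common end) or 31, 29 and 26% (24-month course).

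**Step 4: full grid.** Common end or 48 months: 31-100% on treatment at the cutoff and 24-74% of treatment time after it. Courses ending at Month 24: 19-90% and 10-53%. The low ends come from front-loaded enrolment starting 01 Apr 2017 with 30% retention.

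**Step 5: by-visit endpoints.** The CGI-S shifts are summarised "by descriptive statistics at 1, 3, 6, and 12 months". In the central case the share of *before* visits on or after the cutoff is 28m/1021 for study month m: 2.7, 8.2, 16.5 and 32.9% at Months 1, 3, 6 and 12. Mixing is small early and grows. Across enrolment shapes and start dates, Month 12 ranges from 10 to 57%.

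**The case against.** The strongest reply is that the appendix calls this a subgroup analysis and defines its groups openly as enrolment cohorts. It never says that the first group's events happened before March 2020. New regions act through enrolment, so a cohort split is a natural choice. The appendix already limits itself to description, judges the impact limited and admits confounding. On this view the fault is a poor column header and an unstated limitation.

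Much of that stands, and it is why the point is minor. It does not remove the mismatch, because the stated purpose is to explore the pandemic's impact. For event-type items a cohort contrast does not do that, and none of the admitted limits covers follow-up of earlier enrolees into the pandemic.

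Three further objections also stand.
- A reader might infer that every pre-cutoff enrolee who had not discontinued was still on treatment at the cutoff. The documents do not support this. Treatment may end at regulatory action, Protocol 7.3 defines early termination as before Visit 25 (Month 24), and SAP 3.7.3 plans summaries for completers at 24, 36 and 48 months. Shorter courses were therefore contemplated.
- Calendar classification has its own confounding: later calendar time is also later treatment time, from subjects who stayed.
- Labelling by-visit endpoints by calendar date would gain little. Early months are barely mixed, and a subject enrolled on 01 Apr 2017 has only 1065 days before the cutoff. With Month 39 due on Day 1093 (SAP Table 10), there would be no scheduled pre-cutoff visits from then on.

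**Conclusion.** The point holds for TEAEs, SAEs, protocol deviations and discontinuations. Followed as written, the *before pandemic* column includes pandemic-time events, so for these items the contrast cannot be read as before versus during.

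The direction is secure, since it follows from the grouping rule and the treatment length. The size is not known. The ranges (24-74% of *before* treatment time after the cutoff with treatment to the common end or 48 months, 10-53% with 24-month courses) rest on assumed enrolment shapes, start and end dates and retention. The actual number of misplaced events cannot be derived from the documents.

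A reader might also infer that a pandemic effect exists and is being hidden, or that the SAP is wrong to call the impact limited. The documents support neither; the SAP bases that judgement on its review of deviations. Baseline data are correctly split by enrolment. Severity is minor.

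**What to change.** 1. Keep the enrolment-date split for demographics and baseline characteristics, with columns labelled as enrolled before, and enrolled on or after, 01 Mar 2020. This also assigns 01 Mar 2020 itself, which the present wording leaves in neither group.
2. For TEAEs, SAEs, deviations and discontinuations, classify each event and the person-time at risk by its own date as before or on/after 01 Mar 2020. Report rates per 100 person-years in each period.
3. Flag events whose partial start date could lie on either side. Under SAP 6.2, partial start dates of "adverse events will be assumed to be the earliest possible date consistent with the partial date", so an onset known only as 2020 becomes January 2020 and would count as before. This issue arises only with date-based classification.
4. Leave by-visit endpoints by enrolment cohort, labelled as such.
5. State in the appendix that subjects contribute to both periods, and that calendar period remains partly confounded with time on treatment, persistence and new regions.

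The cost is a revised appendix and modest programming on dates already collected. If the tables already exist, the least that should be done is to relabel the columns as enrolment cohorts and state that earlier enrolees were followed past the cutoff.
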